Aim 2: We will conduct 2 nonrandomized open pilots (30 patients total, 15/arm) of the refined *Active Brains-Fitbit* versus the refined Active Brain for patients with chronic pain and MCI or MRP. We will collect quantitative survey and exit interview data about feasibility, acceptability, and credibility. We will also compare the credibility, feasibility, usability and adherence between the 2 treatments as well as all study procedures in preparation for an efficacy trial.

Specific aims for phase III are:

Aim 3: We will conduct a virtual randomized controlled trial of the Active Brains-Fitbit program versus an education control (Health Enhancement Program) in chronic pain patients with MCI or MRP (N = 40 total; 5-8/group). We will collect quantitative survey and exit interview data about feasibility, acceptability, and credibility. We will use data to further refine the programs. We will compare the credibility, feasibility, usability and adherence between the two programs, *Active Brains-Fitbit* and the HEP, as well as all study procedures in preparation for an efficacy trial.

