Prior to enrollment, interested participants will contact study staff for more information about participation. A research assistant will provide study details to participants and screen for eligibility via phone. Participants will be asked to self-report if they have any memory problems, such as problems forgetting names, events, getting lost, or having to re-read information over and over, as well as their future availability to attend the program. Additionally, those who express interest and wish to participate in the study will review the consent form briefly with a member of study staff via phone during the initial screening conversation. The study staff will continue to follow-up with interested participants via phone until a date for the groups have been selected (group times are based off the majority of participants' availability). Once a date and time for the groups has been selected, a member of study staff will email participants the consent form 2-3 weeks prior to the baseline session.

After consenting, participants will set up a time with a member of study staff to download Zoom and to learn how to use the platform, in order to see all participating members of the group. Zoom specifically states that their software is equipped to keep information secure and the software does not have access to identifiable information. Zoom is HIPPA compliant, Partners approved, and the current video software standard for patient care within our Department of Psychiatry.

A member of study staff will mail the accelerometer (ActiGraph, used in Phase II) with detailed instructions on how to use and wear the device after the consent form is received with detailed instructions on how to wear the device and when to start and stop wearing the device. Participants will be provided with a return shipping label and packaging. All participants will wear an accelerometer for 7 days before the first treatment session (baseline) and for 7 days after the final treatment session (post-test).

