Next, participants will be emailed links to complete several baseline questionnaires via REDCap. If requested by the participant, questionnaires will be administered by trained research assistants over Zoom using the screen-sharing tool. The research assistant will be responsible for scheduling a participant-preferred time to complete the REDCap questionnaire over Zoom. Participants will be advised they must complete the REDCap survey within one week to ensure that the assessment accurately captures their current functioning. Study staff will call participants up to three times if the participant has not completed the questionnaires 3 days before the due date. Upon completion of the questionnaires, a trained member of study staff will set up a Zoom meeting for the completion of the MoCA, in which the participant will be asked to have a piece of paper and pen or pencil ready before the meeting to display on screen, then the member of study staff will ask the participant to hold up the paper, without their face in frame and take a screenshot of the completed assessment. After completion of the MoCA, a member of study staff will assist the participant with downloading the 6-minute walk test (6MWT) application (*Timed Walk*) on their smart phone that the participant will complete on their own, or with a caregiver and by the requested date from the member of study staff. The *Timed Walk* application, used here for the 6MWT, available on iOS and Android devices has shown to be a valid measure of physical function and a reliable alternative to in-person assessments. Participants will be informed during the consent process and again during the downloading process of this application with a member of study staff that the application will retrieve both GPS location and number of steps taken while completing the assessment. Participants will be told not to save their walk history on the application to maintain privacy and will be asked to instead screenshot or write down the number of steps taken as told by the application to then inform study staff. Study staff will inform participants that they do not have to use the application again until post-test, at which after post-test is complete they may delete the application.

The same procedures for the baseline assessments (accelerometer and REDCap) will be repeated for the post-testing.

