Once questionnaires, MoCA, and the 6MWT have been completed, participants will be assigned to one of the two groups using a randomized block design (in blocks of 12 via [sealedenvelope.com](http://sealedenvelope.com)), to ensure that equal numbers of patients are split into the *Active Brains-Fitbit* or the HEP groups. Participants will be notified via email which group they have been assigned to. They will be told that they can participate in one of 2 programs, Active Brains 1 (which is the active intervention) or Active Brains 2 (which is the control group). If participants are assigned to the *Active Brains-Fitbit* group, a study staff will mail a Fitbit device with instructions to the participants. Participants will not be expected to pay for the device or any shipping costs.

One week prior to the start of the group, a research assistant will email all participants to begin wearing the accelerometer device. The research assistant will check-in with all participants via Zoom or phone the same day in order to ensure that there are no technological problems, as well as confirm that all participants are wearing the device properly. The study staff will continue to check in with participants throughout the one-week wear period to ensure adherence. After the one-week period, participants will be asked to return the ActiGraph device using the pre-paid shipping label and packaging provided. Participants will be asked to confirm that they have returned the device via mail. Following the one-week ActiGraph period,

all participants in the *Active Brains-Fitbit* group will pair their FitBit DMD to a smartphone with Bluetooth. A research assistant will schedule a time with all participants to provide guidance via Zoom on how to sync their Fitbit device to their personal phone. Participants in the *Active Brains-Fitbit* group will begin wearing their device for the duration of the program once the device is synced to the participant's phone.

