Time-Matched Attention Placebo Active Comparison Condition: Health Enhancement Program (HEP). The active comparison condition controls for the effect of “time spent”, “group member support/feedback” and “interventionist support/feedback” and includes delivery of educational information on MCI/MRP and chronic pain symptoms drawn from reputable websites, and standard healthy living information drawn from the Center for Disease Control recommendations and standards for health promotion (e.g., “Sleep”, “Nutrition”, “Healthy Weight”, and “Medical appointments”). Such control interventions are routinely used in stringent RCTs of psychosocial interventions. The HEP program consists on 8 group sessions (each session is 90 minutes) that occur concurrently with the active intervention condition, *Active Brains-Fitbit*. The active comparison HEP is conducted in the same format as the intervention condition but does not include any relaxation response, cognitive behavioral or positive psychology skills training that are reflected in the *Active Brains-Fitbit*. Patients in the HEP receive the same attention from the study therapist as those in the *Active Brains-Fitbit*.

To prevent participant unblinding, participants will be asked not to share specific information discussed in the group (e.g., skills learned, topics discussed) on social media sites (e.g., Facebook groups or internet chat groups) or with other acquaintances for the duration of the study.

During enrollment, participants have the option to consent to receiving reminders in the form of phone calls, text messages, or email over the course of the intervention, depending on personal preference. Participants will be informed of texting risks and provide consent for text messaging in writing or verbally if preferred. Participants will have the opportunity to ask questions about texting with study staff. Approval of text messaging and/or opting out of text messaging will be recorded in each participants file. Between session contact will focus on increasing treatment adherence, maintaining engagement, and session reminders. Text messages will be sent once or twice a week for the duration of the study. Participants may opt-out of the text message contact option at any point.

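### In Phase III the baseline accelerometer week comes after participants are told their arm and one arm is mailed a Fitbit, so baseline activity and wear days may reflect allocation

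*Protocol*

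**What the plan says.** All of the following comes from the Protocol, Study Procedures, Phase III, unless stated otherwise.

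- The ActiGraph is mailed after consent. Baseline wear is defined as "for 7 days before the first treatment session (baseline").
- Links to the baseline questionnaires come next. Participants are told "they must complete the REDCap survey within one week". The MoCA and then the app-based 6-minute walk test follow.
- Allocation comes after these three assessments: "Once questionnaires, MoCA, and the 6MWT have been completed, participants will be assigned to one of the two groups". Accelerometer wear is not among the conditions.
- Allocation is then disclosed: "Participants will be notified via email which group they have been assigned to". The two programmes carry the labels Active Brains 1 and Active Brains 2.
- For those assigned to Active Brains-Fitbit, "a study staff will mail a Fitbit device with instructions to the participants".
- The wear week is described after this: "One week prior to the start of the group, a research assistant will email all participants to begin wearing the accelerometer device". Staff check in with everyone during the week, the ActiGraph goes back, and only then is the Fitbit paired and worn.

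The SAP (Analyses plan, Aim 2) reports accelerometer wear days at baseline and post-test in both groups. It also reports within-group percent change in quantitative outcomes, which include steps and active minutes, and describes sedentary time before and after. It plans no efficacy analysis.

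**The concern.** A baseline measure should be complete before the participant can know the arm. Here the questionnaires, MoCA and walk test meet that standard and the accelerometer does not. What it records is walking activity, which one arm is about to be coached to increase. The Protocol itself describes the Fitbit as a means of motivating and reinforcing activity (Background, section 1.5) and lists recent regular Fitbit use as a treatment confound (Subject Enrollment, exclusion criteria).

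A participant who has received a Fitbit and instructions might start walking more, or might hold back until the programme begins. A participant who knows they are in the control programme might be less careful about wearing the ActiGraph. The direction cannot be predicted. Any such response enters the denominator of the percent change in steps and active minutes, the pre/post description of sedentary time, and the comparison of wear days by arm.

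**Working it through.** The plan has no figure of its own to reproduce on this point. The check is one of sequence, followed by a sensitivity calculation.

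**Sequence in the Phase III text**

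1. Consent
2. ActiGraph mailed
3. REDCap questionnaires (up to 7 days)
4. MoCA
5. 6-minute walk test
6. Randomisation
7. Assignment email
8. Fitbit mailed to one arm
9. ActiGraph baseline week (7 days)
10. ActiGraph returned, Fitbit paired and worn

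Step 9 follows steps 6 to 8 in the narrative, and three features of the text support that reading. Wear is not a condition for randomisation. The wear week is the last week before the first session. The Fitbit is paired directly after the wear week, and it cannot be mailed to one arm until allocation is known. No statement in either document puts wear before disclosure.

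**Sensitivity of the reported percent change**

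Let *g* be the true change in an arm from its undisturbed baseline to post-test. Let *b* be the proportional shift in that arm's mean baseline caused by knowing the allocation. If the post-test value is unaffected by *b*, then

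reported change = (1 + *g*)/(1 + *b*) − 1.

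Both *g* and *b* are assumed; the documents supply neither.

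| | *b* = −10% | *b* = −5% | *b* = 0 | *b* = +5% | *b* = +10% |
|---|---|---|---|---|---|
| *g* = 0 | +11.1% | +5.3% | 0.0% | −4.8% | −9.1% |
| *g* = 10% | +22.2% | +15.8% | +10.0% | +4.8% | 0.0% |
| *g* = 20% | +33.3% | +26.3% | +20.0% | +14.3% | +9.1% |

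Example: *g* = 20%, *b* = +10% gives 1.20/1.10 − 1 = 9.1%, an error of −10.9 points. With *b* = −10% it is 1.20/0.90 − 1 = 33.3%, an error of +13.3 points.

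Across the table the absolute error runs from 9.1 to 13.3 points at a 10% shift and from 4.8 to 6.3 points at a 5% shift.

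**Room in the schedule**

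The consent form is emailed 2 to 3 weeks (14 to 21 days) before the baseline session. Questionnaires followed by wear take up to 7 + 7 = 14 days; run side by side they take 7. These totals leave out Zoom set-up, shipping, the MoCA and the walk test, so they show only that overlapping the two windows saves up to a week.

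**The case against.** The strongest case against has four parts.

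- **The order is not dated.** The Phase III text describes the ActiGraph mailing and the wear week before it turns to the questionnaires, and later groups accelerometer and REDCap together as baseline assessments. The start of the group, the baseline session and the first treatment session are not clearly the same date. This stands as an ambiguity. It does not reverse the reading, because wear is still tied to the week before the first session and the start email is described after assignment.
- **Safeguards exist.** The Fitbit is not used until the wear week is over, participants may see only neutral programme labels, and staff check in with both arms. These remove direct Fitbit feedback and some of the risk of uneven wear. They do not hide the assignment email or a Fitbit arriving by post.
- **The harm is small here.** There is no efficacy analysis and no planned between-arm comparison of steps, and the criterion of 6 of 8 sessions is unaffected. The SAP is written for Active Brains with Fitbit against Active Brains, so applying its outcome list to Phase III, which compares with HEP, is an inference. The ±10% range has no source in the documents. All of this is correct and limits the weight of the point.
- **Wear days are adherence data, and a late baseline is more current.** Wear counted under a known allocation is a valid count, but a difference between arms could then come from disclosure. A wear week just before treatment does give the most recent activity level, and moving it forward gives up some of that.

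**Conclusion.** The concern holds. As written, Phase III collects its accelerometer baseline after allocation has been disclosed and after one arm has been sent a Fitbit. The conclusion rests on the order of the narrative and on wear being absent from the conditions for randomisation, not on stated dates.

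The size and direction of any effect are unknown. The shifts of 5% and 10% in the table are assumptions that show sensitivity and do not estimate a bias; if knowing the arm changes nothing, the error is zero.

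The consequence for the pilot's own conclusions is limited to descriptive accelerometer summaries, assuming the SAP's outcome list is applied to Phase III. The point is still worth fixing, because Aim 3 examines the two programmes "as well as all study procedures in preparation for an efficacy trial". In that later trial the same order would affect a between-arm comparison of objective activity. This is an avoidable weakness that should be corrected, not one that invalidates the study.

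**What to change.** Complete the 7-day ActiGraph week before allocation is disclosed. The device is already mailed before the questionnaire links go out, so wear can run alongside the one-week REDCap window. Randomise, or at least send the assignment email and mail the Fitbit, only once the wear window has closed. Closure should depend on the calendar and not on whether the participant wore the device. Non-wearers then stay in the randomised sample, and wear days can still be reported by arm.

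Two places in the Phase III procedures need matching edits: the definition of baseline wear as the week before the first treatment session, and the instruction that starts wear one week before the group.

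If the present order is kept, record the dates of the assignment email, Fitbit delivery and wear start for each participant. Label the accelerometer baseline as post-allocation, and state the limitation wherever steps, active minutes, sedentary time or wear days are reported.

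**Cost.** No new visit, device or assessment is needed. The group date is set before the consent form is emailed, and HEP sessions are ones "that occur concurrently with the active intervention condition", so later disclosure should not disturb group scheduling. The pre-group schedule may have to start about a week earlier so that the ActiGraph arrives in time, and the baseline will be somewhat further from the first session. If the wear week stays where it is and only disclosure moves, there is less time to mail and pair the Fitbit before the first session.

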## V. BIOSTATISTIC ANALYSIS

### Phase I:

The qualitative focus group data and individual exit interview data will be transcribed and analyzed, using NVivo 10 qualitative software, and we will conduct thematic content analysis using guidelines provided by Miles and Huberman (1984). The 2 coders ([name] and study clinician) will meet on an ongoing basis with [name] to discuss the structural thematic

framework, categories, and coding plan. To ensure coding reliability, coding discrepancies will be resolved through discussion and comparison of raw data. Coding will continue until a high reliability (Kappa= >0.80) is established. Once these data analyses are completed, the multidisciplinary team will provide the expert review of data, to discuss the interpretation of our findings in the context of current research on chronic heterogeneous pain.

#### Phase II/Phase III:

The *Active Brains-Fitbit* group will use a Fitbit DMD through which participants will use Fitbit accounts with deidentified physical measurements (i.e. height and weight) and profile information with approximate birthdays (e.g. month and year only). Participant account names will be set up with “Participant” as the first name and study ID # as the last name. De-identified DMD data will be processed securely through the Fitbit data collection company, Fitabase. Fitabase does not store identifiable data and all participant data is uploaded through encrypted server communication and stored in a highly secure unfractured. [name] has used Fitabase in previous mind-body intervention studies, including in the current NCCIH R34. The qualitative interview data will be transcribed and analyzed, using NVivo 10 qualitative software, and we will conduct thematic content analysis using guidelines provided by Miles and Huberman (1984). Coders will meet on an ongoing basis with [name] to discuss the structural thematic framework, categories, and coding plan. To ensure coding reliability, coding discrepancies will be resolved through discussion and comparison of raw data. Coding will continue until a high reliability (Kappa= >0.80) is established. Once these data analyses are completed, the multidisciplinary team will provide the expert review of data, to discuss the interpretation of our findings in the context of current research on chronic pain, MCI, and MRP.

## **VII. RISKS AND DISCOMFORTS**

Patients will be informed that there are no foreseeable physical risks from this research study. They will be informed that in the unlikely situation that they might feel uncomfortable with the topic of discussing within the group, they can alert the group leader who will provide help, as needed. The group leaders are experienced clinical psychologists. They will also be informed that they may feel uncomfortable completing various psychological questionnaires and that they may find it time-consuming to participate in weekly 90-minute groups.

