### I. BACKGROUND AND SIGNIFICANCE

**1.1 Chronic pain and Mild Cognitive Impairment (MCI) are highly prevalent among older adults and independently associated with decreased emotional and physical function.** Approximately one third of older adults experience pain daily. In older adults, chronic pain is associated with substantial disability from reduced mobility, avoidance of activity, falls, depression and anxiety, sleep impairment, and isolation. Its negative effects extend beyond the patient, to disrupt both family and social relationships. Patients with chronic pain also report non-adaptive coping strategies with pain catastrophizing and fear of pain being the most salient, and both associated with decreases in physical and emotional function. Prevalence rates for pain are expected to increase as populations continue to age—by 2035 an estimated one quarter of the population in the European Union will be 65 or older—thereby increasing the public health impact of pain. As a consequence, NCCIH has designated chronic pain as a national priority area. Mild cognitive impairment (MCI) – a decline in cognitions, including memory, communication, concentration and orientation over what is considered normal aging, is also prevalent, with 1 in 5 older adults reporting symptoms of MCI. MCI is the intermediate stage between the cognitive changes of normal aging and dementia. Individuals diagnosed with MCI show cognitive impairment greater than expected for their age, but otherwise are functioning independently and do not yet meet the criteria for dementia. MCI is associated with decreased mobility, and physical function, and high distress.

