relationship between daily physical activity such as a 30-minute walk and several health related outcomes such as mortality, cardiovascular diseases and cancer. Patients with chronic pain and MCI are sedentary and take significantly fewer steps per day than an average healthy adult. Although exercise is one of the recommended treatments for MCI patients with documented cognitive benefits, few successfully engage in these programs. Deconditioning is common in chronic pain, can be a significant risk factor for *further* pain conditions and disability. Aerobic exercise has been shown to be the mainstay of chronic pain treatments for multiple, heterogeneous pain conditions including low back pain, fibromyalgia, and chronic myofascial conditions, with walking being the most commonly prescribed, but adherence being problematic. When walking is quota-based (i.e., not contingent on pain level), results are even more promising. Prior research has identified barriers to engaging and adhering to physical exercise in chronic pain, which included decreased mood, pain, coping difficulties (e.g., fear avoidance, catastrophic thinking about pain), programs that were too challenging (e.g., going to the gym), not meaningful, interfering with one's life, or too difficult to implement. Focus groups and qualitative interviews with older adults with chronic pain have consistently showed that walking is the preferred method of physical activity in this population. **Despite the aforementioned benefits of physical activity for chronic pain and MCI physical activity including walking are not addressed or assessed in mind body programs.**

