#### IV. SUBJECT ENROLLMENT

Interested participants who meet study criteria will be consented and then scheduled to participate in one of the focus groups (in Phase I) or intervention groups (in Phase II). See Table 1.

Table 1	
Patient Inclusion Criteria	Rationale
Male and female outpatients, age 60 years or older	Population under study
Have nonmalignant chronic pain for more than 3 months	International Association for Study of Pain (IASP)  criteria

Has MCI or memory-related problems (MRP) (forgetting names, getting lost, forgetting obligations)	Population of study
Able to perform a 6-minute walk test at an accelerated pace	Program will involve increase number of steps/outcome measure
Free of concurrent psychotropic or pain medication for at least 2 weeks prior to initiation of treatment, OR stable on current psychotropic or pain medication for a minimum of 6 weeks and willing to maintain a stable dose	Treatment confound
Cleared by a medical doctor for study participation	Human subject concern, risk
Owns a smartphone with Bluetooth 4.0	Necessary for pairing with DMD and storing/downloading data.
Caregiver Inclusion Criteria (Phase I only)	Rationale
Caring for someone with mild cognitive impairment and chronic pain	Population of study
Currently living with someone with mild cognitive impairment and chronic pain	Population of study
Patient Exclusion Criteria	Rationale
Diagnosed with a medical illness expected to worsen in the next 6 months (e.g., malignancy)	Treatment confound
Serious mental illness or instability for which hospitalization may be likely in the next 6 months	Feasibility, participant safety
Current suicidal ideation reported on self-report	Subject safety
Lifetime history of schizophrenia, bipolar disorder, or other psychotic disorder	Treatment confound
Current substance abuse or dependence and current substance use disorder, within the past 6 months	Treatment confound
Practice of yoga/meditation, or other mind body techniques that elicit the RR, once per week for 45min or more within the last 3 months or less	Treatment confound
Regular use of Fitbit in the last 3 months.	Treatment confound
Engage in regular intensive physical exercise for more than 30 minutes a day	Treatment confound
Unable to walk without use of assistance (e.g. walker, cane, wheelchair)	Treatment confound

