Participants will also give feedback about the assessments and whether they capture aspects important to them, and we will refine the length, timing, and content of these as needed. We will ask specific questions about any problems with adherence to *Active Brains* and *Active Brains-Fitbit* homework. Questions will also be asked about the therapeutic alliance with the group leader, and the extent to which participants felt connected and understood by the group leader. Finally, we will ask questions about the best approaches for participant recruitment and retention. [name] has used these types of procedures in other mind-body intervention studies. Information from qualitative interviews will be corroborated with information from the satisfaction and the credibility questionnaires and will serve to refine the intervention for the next phase.

During enrollment, participants have the option to consent to receiving reminders in the form of phone calls, text messages, or email over the course of the intervention, depending on personal preference. Participants will be informed of texting risks and provide consent for text messaging in writing or verbally if preferred. Participants will have the opportunity to ask questions about texting with study staff. Approval of text messaging and/or opting out of text messaging will be recorded in each participants file. Between session contact will be used with the goal of increasing treatment adherence and engagement and session reminders. Text messages will be sent once or twice a week for the duration of the study. Participants may opt-out of the text message contact option at any point.

Participants in the *Active Brains-Fitbit* group will pair their Fitbit DMD to a smartphone with Bluetooth, and the Fitbit will inform an individualized quota-based behavioral plan to improve both adherence and efficacy. All participants will also wear an accelerometer for 7 days at baseline and at the end of the intervention. Participants will be compensated \$30 for each assessment completed, and \$10 for transportation (for each visit). Participants may earn up to \$160.

Phase III:

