The groups will be conducted virtually by a trained study therapist via Zoom over 10 weeks, which includes 8 group sessions and 2 assessment sessions. Each session will last approximately 90 minutes. Participants can attend the online group sessions from your own home or any other private place with a personal computer. The personal computer must be equipped with a webcam and Zoom videoconferencing software. If needed, members of the research team will contact participants by phone to assist with study-related tasks (e.g., provide technical support to facilitate use of technology). Participants will be invited to participate in an optional focus group exit interview one week after participants have completed the post-test assessments.

In *Active Brains-Fitbit*, participants learn (1) walking skills to gradually average increase through SMART goal-setting, individualized non-pain contingent quota-based pacing (e.g., walk for 30 minutes or meet a step goal of 5,000 steps), and engagement in meaningful activities; (2) mind–body skills to reduce reactivity and catastrophizing to pain or fear of cognitive decline through diaphragmatic breathing body scanning and mindfulness exercises; (3) pain–cognition awareness skills to correct misconceptions about chronic pain and MCI/MRP that may impede participation and understand the disability spiral (e.g., how sedentariness perpetuates chronic pain and MCI/MRP); (4) cognitive functioning skills to develop cognitive compensatory strategies and increase intellectual stimulation; and (5) social and emotional functioning skills to manage negative reactions from others and cope with stress or walking setbacks (positivity, self-compassion, and gratitude). Subjects will be encouraged to complete their homework (logs for mind–body practice, physical activities, and gratitude) each day.

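### Section VII tells patients, with no phase limit, that no physical risk is foreseen, which does not fit the walking program and walk test of Phases II and III

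*Protocol*

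**What the plan says.** Protocol Section VII (Risks and Discomforts) is one paragraph with no phase label. It opens: "Patients will be informed that there are no foreseeable physical risks from this research study". The only burdens it goes on to list are unease with group topics, unease with questionnaires, and time: "they may find it time-consuming to participate in weekly 90-minute groups".

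Elsewhere the protocol describes physical activity that participants are asked to do:

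- Study Procedures, Phase II: for the Active Brains-Fitbit group, "the Fitbit will inform an individualized quota-based behavioral plan to improve both adherence and efficacy".
- Study Procedures, Phase III: the Active Brains-Fitbit arm is taught "individualized non-pain contingent quota-based pacing (e.g., walk for 30 minutes or meet a step goal of 5,000 steps".
- Study Procedures, Phase III: the six-minute walk test runs on a phone app "that the participant will complete on their own, or with a caregiver".
- Section IV, eligibility table: "Able to perform a 6-minute walk test at an accelerated pace".

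The same eligibility table requires clearance by a doctor, and its rationale column gives risk as part of the reason.

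**The concern.** A flat statement that no physical risk is foreseen is reasonable for a focus group. It is hard to reconcile with a program whose purpose is to raise walking in older, inactive people with chronic pain, and to keep that walking going when it hurts. If the consent conversation follows Section VII as written, people with pain and memory problems would hear of no physical risk before they join the walking program or do a walk test without staff present. What is at stake is accurate risk information and participant safety. The estimates and the feasibility criterion are not involved.

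**Working it through.** No formula applies, and the plan has no figure to reproduce. The check compares the sentence with the rest of the text and counts whom it reaches.

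**1. Does the sentence reach beyond Phase I?** Yes. Sections V and VIII are split into Phase I and Phase II/Phase III; Section VII is not. Its reference to weekly 90-minute groups matches the Phase III session length and the weekly program format, not a focus group. The Potential Benefits section that follows it names Phase III and lists greater physical activity as a possible gain.

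**2. Does the intervention involve exertion that is not limited by pain?** Yes. Section 1.4 defines quota-based walking as walking that does not depend on pain level. Phase II applies a quota-based plan in Active Brains-Fitbit. The session table in Section 3.2 proposes raising activity whatever the pain (session 1) and keeping to the step goal despite pain (session 5). That table is proposed content, open to change after the focus groups, but the Phase III text keeps the principle, with examples of 30 minutes or 5,000 steps.

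**3. Does the protocol itself anticipate physical setbacks?** Yes. The session table includes coping with pain flare-ups (session 5) and staying resilient through flares (session 8). Phase III teaches participants to cope with setbacks in walking. A flare that the sessions prepare people for is foreseen by the protocol.

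**4. Who are the participants?** They are 60 or older, with chronic pain and MCI or memory problems. Section 1.1 says that in older adults "chronic pain is associated with substantial disability from reduced mobility, avoidance of activity, falls, depression and anxiety, sleep impairment, and isolation". Section 1.4 says "Patients with chronic pain and MCI are sedentary and take significantly fewer steps per day than an average healthy adult".

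**5. Is the walk test supervised?** In Phase III, not by staff. The participant does it with the app, alone or with a caregiver, and the app is used again at post-test. The baseline test precedes randomisation, so everyone entering Phase III is asked to do it, including those later assigned to the education control. The accelerated pace is stated in the eligibility table and is not restated in the Phase III procedure.

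**6. Reach** (counts from Section II):

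- Intervention phases: 30 (Phase II) + 40 (Phase III) = 70.
- Clearly assigned quota-based walking: 15 (Phase II Active Brains-Fitbit) + 40/2 (Phase III Active Brains-Fitbit) = about 35.
- If Phase II Active Brains without Fitbit also carries walking goals, which Section 3.2 leaves open by saying that it follows the same framework: 30 + 40/2 = about 50.
- Asked to do the app-based walk test: all 40 in Phase III.

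These are numbers of people covered by the statement. They say nothing about how often harm would occur.

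**The case against.** The strongest reply has three parts.

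**Safeguards.** Entry requires a doctor's clearance, stable or no relevant medication, and the ability to do the walk test. People who cannot walk unaided or whose illness is expected to worsen are excluded. Section 1.5 describes goals fitted to each patient's ability and raised gradually. All of this stands, and it supports calling the risk low. It does not support calling it unforeseeable, and requiring clearance partly because of risk points the other way.

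**Evidence.** Section 1.1 associates falls with chronic pain; it does not attribute them to walking. Section 1.4 presents deconditioning as a danger and quota-based walking as promising. A reader might infer that the documents show the program causes falls or injury. They do not, and they give no event rates. The point needs only that flares, strain and falls can be foreseen when such participants walk more.

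**Unseen text.** The consent form was not available, and other disclosures (app location data, texting risks) sit outside Section VII, so that section is not the whole of what patients hear. A reader might infer that participants were in fact left uninformed. That cannot be established. What can be said is that the protocol's own statement of what patients will be told is inaccurate for Phases II and III.

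A reader might also conclude that adverse events go uncollected, and ask for a routine question on falls and flares with results by arm. The documents do not support that as a required change. The supplied text has no Section VI or IX, so missing event capture is not shown. Repeated prompting about pain is also debatable in a program that teaches less vigilance to pain, when catastrophizing and fear avoidance are among the SAP's outcomes.

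**Conclusion.** The point holds as a minor wording correction. Section VII's statement is sound for the Phase I focus groups and inaccurate for Phases II and III, where it conflicts with the protocol's own session content, walk-test procedure and clearance rationale. It covers 70 intervention-phase participants. No estimate, feasibility threshold or statistical conclusion changes.

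The conclusion rests on reading Section VII as covering all phases, which its wording supports. Describing the risk as low is a judgement based on the safeguards, since the documents contain no rate to measure it by. Any practical harm depends on whether the consent form repeats the sentence, which is unknown.

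**What to change.** Limit the present sentence in Section VII to the Phase I focus groups. For Phases II and III, replace it with a statement that there is a low but foreseeable risk of a temporary increase or flare in pain, of musculoskeletal strain, and of falls or exertion during walking and the walk test. The existing safeguards can be named alongside it. Check the consent form and align it if it carries the Section VII sentence.

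The cost is a text amendment and a slightly less reassuring risk statement. The walking program, assessments, sample size and analysis stay as they are.
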